#### 2) MLAS

Participants in the intervention group can only attend MLAS if they have attended a structured stroke review. A linear mixed effect model will be fitted in line with the primary analysis with fixed effects for gender, baseline score and categorical variable MLAS compliance (yes, partial, no), where

- Complete an individual attended both individual appointments and at least 3 of the 4 group sessions (including group session 1).
- Incomplete an individual has attended at least 1 session (either an individual appointment or group session).
- No an individual has not attended any MLAS sessions.
- 3) Intervention fidelity

The trial team will collect data on intervention fidelity (Table 4) to monitor exposure and quality of various aspects of the intervention as follows:

 Fidelity of training – Audio-recorded training sessions (IPCAS) will be scored against a prespecified checklist containing planned curriculum content and materials (n= 16 items). Three response options are used: done (2 points), partially done (1 point) and not done (0 points). Video-recorded training sessions (MLAS) will be scored against a pre-specified checklist containing planned curriculum content and materials (n= 205 items). Three response options are used: present (2 points), attempted (1 point) and absent (0 points).

- Fidelity of delivery Audio-recorded structured reviews will be scored against a pre-specified checklist (n= 9 items). Three response options are used: done (2 points), partially done (1 point) and not done (0 points). Self-reported structured reviews will be scored against a pre-specified checklist (n= 9 items). Three response options are used: done (2 points), partially done (1 point) and not done (0 points). Checklist data will be summarised using descriptive statistics (i.e. proportions, means). Data relating to the 15-item checklist of needs will be summarised using descriptive statistics (i.e. proportions, frequencies, means), and outliers may be excluded as a sensitivity summary. Action plans (i.e. referrals/advice/further appointments) made during the structured review will be summarised using descriptive statistics (i.e. proportions, frequencies, means).
- Fidelity of receipt Self-reported experience of structured reviews will be scored against a
  pre-specified checklist (n= 9 items). Three response options are used: done (2 points),
  partially done (1 point) and not done (0 points). Self-reported experience of MLAS will be
  scored using a set of questionnaires (6 questionnaires in total; 74 items). Four response
  options are used: agree, disagree, don't know, does not apply. Checklist data will be
  summarised using descriptive statistics (i.e. proportions, means).

Inter-rater reliability of fidelity of training and delivery data, specifically observations and audio-recordings will be assessed using percent agreement and Cohen's Kappa (95% CI):

$$\kappa_w = \frac{\sum v_{ij} \, p_{oij}}{\sum v_{ij} p_{eij}}$$

Where,

 $\kappa_w$ = agreement value (-1 to +1 ,where +1 represents perfect agreement between raters)  $v_{ij}$ = disagreement weight (quadratic weights)  $p_{oij}$ = is the proportion of the joint judgements

 $p_{eij}$  = is the proportion of judgements expected by chance

Intervention fidelity scores between 80-100% are classed as 'high', 51-79% 'moderate' and <50% as 'low'.

**Table 4**: Intervention fidelity components collected from participants and practices.

Intervention components	НСР	Participant
Structured review	$\checkmark$	$\checkmark$
	Duration/frequency: One-	
	off, up to 30min	
	Mode: Face-to-face	
15-item checklist of needs	$\checkmark$	$\checkmark$
		Sent before structured
		review
My Life After Stroke (MLAS)		$\checkmark$
		Duration/frequency: 6-week
		self-management course (2x
		individual appointments up
		to 45min each; 4x weekly
		group sessions up to 2.5hrs
		each)

		Mode: Face-to-face
Direct point of contact	$\checkmark$	$\checkmark$
service		Duration/frequency: As and
		when required
		Mode: Telephone
Service mapping tool	$\checkmark$	$\checkmark$
	Duration/frequency: As and	
	when required	
Optimised communication	$\checkmark$	
	Duration/frequency: As and	
	when required	
Healthcare professional	$\checkmark$	
training	Duration: Up to 2hrs	
_	Mode: Face-to-face	

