# **10.1 Primary Efficacy Analyses**

The standardised domain total scores will be calculated (as described in section 9.2.1) for each of the two co-primary outcomes (SIS emotional domain and SIS handicap domain). The analyses will focus on the evidence for a difference in SIS score (handicap or emotion) between the intervention and control group.

Each domain will be modelled separately and the following model fitted:

$$Y_i = \beta_0 X_{0i} + \beta_1 X_{1i} + \epsilon_i$$

For each co-primary outcome there is the potential for clustering and therefore a mixed effect model will be fitted with a random effect for general practice and fixed effects for the treatment group to assess the effect of clustering:

$$Y_{ij} = \beta_0 X_{0ij} + \beta_1 X_{1ij} + u_j + \epsilon_{ij}$$

Where,

Yij = continuous outcome SIS score (emotion/ handicap domain)

*i* = individual patient

j = cluster/ practice

 $X_1$  = dummy variable for the intervention treatment group.

X0 = baseline covariates (baseline score, gender, cluster size, time since last stroke at consent)

 $\beta_0$  = intercept which represents the population average SIS score

 $\beta_1$  = difference in score between intervention and control groups at 12 months

 $u_i \sim N_1(0, \sigma_h^2)$  is the cluster-level random practice effect

 $\epsilon_{ii} \sim N_1(0, \sigma_e^2)$  is the residual error

There is an a priori hypothesis that the following covariates may be associated with the co-primary outcomes: gender, age at baseline (categorical), time since last stroke (categorical), general practice list size (the stratifying variable used in the randomisation, split into two categories; <10,500 and  $\geq$ 10,500 patients) and deprivation score (continuous, both at the patient and practice level). Once the primary analysis model is decided, these covariates will be added to assess and changes in treatment effect on the co-primary outcomes.

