#### 1) Structured Stroke Review

There is an *a priori* hypothesis that stroke review attendance and the level of action taken at a stroke review is associated with SIS handicap and emotion 12 month score. A linear mixed effect model will be fitted in line with the primary analysis with fixed effects for the stroke review attendance (y/n), and categorical variable for action taken (no review, review with no action plan, review with action plan).

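### The MLAS dose model's 'No' group pools never-reviewed patients with reviewed non-attenders, so the MLAS contrast carries part of the reviewed versus not-reviewed difference

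*SAP*

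**What the plan says.** SAP 10.2.1 plans dose analyses within the intervention arm, with 12-month SIS emotion and handicap scores as outcomes.

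- **Access to MLAS, 10.2.1 (2):** "Participants in the intervention group can only attend MLAS if they have attended a structured stroke review".
- **MLAS model, 10.2.1 (2):** it is to follow the primary analysis, "with fixed effects for gender, baseline score and categorical variable MLAS compliance (yes, partial, no"). The lowest level means that "an individual has not attended any MLAS sessions". Nothing in that definition concerns review attendance.
- **Primary model covariates, 10.1:** "baseline covariates (baseline score, gender, cluster size, time since last stroke at consent"). Review attendance is not among them, so the MLAS model cannot inherit it.
- **Review model, 10.2.1 (1):** a separate model has a "categorical variable for action taken (no review, review with no action plan, review with action plan"). It rests on the prior hypothesis that "stroke review attendance and the level of action taken at a stroke review is associated with SIS handicap and emotion 12 month score".
- **Route to MLAS in the protocol:** the MLAS leaflet is handed out at the review (7.1.1), and MLAS is opt-in (18.3).

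**The concern.** By the SAP's own rule, MLAS attendance implies review attendance, but non-attendance at MLAS says nothing about review. The 'No' level therefore holds two exposure levels: neither component, and review alone. The plan provides for both kinds of patient, since 'no review' is a level of the review variable and MLAS is optional for those reviewed.

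The omitted variable is tied by rule to the exposure, and the SAP expects it to be associated with the same outcome. Part of any gap between reviewed and unreviewed patients would then be read as an MLAS association. This matters because it is the only model in the SAP that relates MLAS attendance to outcome. MLAS is also a substantial component: two individual appointments and four group sessions of about 2½ hours, run by two facilitators (protocol 7.1.2).

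**Working it through.** **The plan's own figure.** The SAP gives no figure for the MLAS model. The nearest yardstick is the design effect size of 0.33 SD with at least 90% power (SAP 7).

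- Design effect with 20 patients per practice: 1 + ((0.65² + 1) × 20 − 1) × 0.03 = 1.824.
- Effective size per arm: 23 × 20 / 1.824 = 252.3. Power at two-sided 2.5% (sidedness assumed; normal approximation) is 92.9%.
- With 16 per practice after 20% loss, the design effect is 1.653 and power is 89.3%, close to the stated figure.

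Below, 0.33 SD serves only as a scale.

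**What the contrast estimates.** Leaving covariates aside, define within the intervention arm:

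- M = mean of MLAS attenders − mean of reviewed patients without MLAS
- R = mean of reviewed patients without MLAS − mean of never-reviewed patients
- q = never-reviewed share of the 'No' group

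The 'No' mean equals the mean of reviewed patients without MLAS minus q × R. So:

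attenders − 'No' = M + q × R

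The complete versus incomplete contrast is free of this term, because both groups were reviewed.

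**Size, with assumed q and R (SD units).** Neither is in the documents.

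| q | R = 0.10 | R = 0.20 | R = 0.33 |
|---|---|---|---|
| 0.20 | 0.020 | 0.040 | 0.066 |
| 0.35 | 0.035 | 0.070 | 0.116 |
| 0.50 | 0.050 | 0.100 | 0.165 |

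If u is the share of the arm never reviewed and w the share attending any MLAS session, then q = u / (1 − w). Letting both u and w run from 10% to 40% gives q from 0.1/0.9 = 0.11 to 0.4/0.6 = 0.67. The term then runs from 0.01 SD (R = 0.10) to 0.22 SD (R = 0.33).

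**Simulation check.** The setting was 23 practices × 16 patients, ICC 0.03, 1,000 runs, true MLAS effect zero and w = 25% (15% complete, 10% incomplete). The table gives the coefficient for complete attendance.

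| u | R | q | q × R | SAP coding | Reviewed only | Gap |
|---|---|---|---|---|---|---|
| 0.20 | 0.33 | 0.267 | 0.088 | 0.085 | −0.004 | 0.089 |
| 0.30 | 0.33 | 0.400 | 0.132 | 0.142 | 0.011 | 0.131 |
| 0.30 | 0.20 | 0.400 | 0.080 | 0.081 | 0.001 | 0.080 |

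The gap between the two codings matches q × R in each row.

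**The case against.** Several objections carry weight.

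- **The access sentence may be meant as a restriction.** It opens the MLAS paragraph and could signal that only reviewed patients enter the model. The table shells are in a separate file that is not available here. But the SAP does not state a restriction, and its definition of 'No' does not contain one. If a restriction was intended, one sentence settles the main point.
- **Review has its own model.** A reviewed versus not-reviewed difference would be visible beside the MLAS result. That helps the reader, but does not remove q × R from the MLAS coefficient.
- **Uptake may be high.** The review is part of the regular annual review (protocol 7.1.1), with ongoing fidelity support (11.1). If nearly all are reviewed, q is near zero. The documents do not say, and the 'no review' level shows that such patients are expected.
- **The analysis is exploratory.** SAP 10.2 says so, and only the co-primary outcomes are powered. That limits the seriousness of the point.

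Some stronger readings are tempting but not supported:

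- *The MLAS coefficient absorbs the whole review effect.* Only the fraction q of R enters.
- *The bias must favour MLAS.* R mixes effect with selection. Patients with more needs might be the ones who attend, and R would then be negative.
- *The MLAS model discards time since stroke, age and deprivation.* Time since stroke is in the primary model list and may be inherited. Age and deprivation are not in the primary equation either: SAP 10.1 adds them afterwards, although SAP 8.3 lists them for the co-primary models.
- *The SAP claims a causal effect of review or of dose.* Its hypotheses are worded as associations.

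**Conclusion.** The point holds as a defect of specification in an exploratory, within-arm model. As written, the attender versus 'No' contrast equals M + q × R. This follows from the SAP's own definitions and needs no assumption beyond some 'No' patients being unreviewed and R being non-zero, both of which the SAP anticipates.

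The size cannot be established from the documents. The illustrative 0.02–0.17 SD rests on assumed q of 20–50% and R of 0.10–0.33 SD. Its top end sets R at the target effect for the whole package, which is generous.

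A reader might infer that the trial's main result is at risk. It is not: the co-primary comparison is by randomised arm, does not use MLAS attendance, and keeps its power.

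**What to change.** Before the final analysis, amend SAP 10.2.1 (2) in one of two ways:

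1. Use a single nested exposure (no review; review, no MLAS; review + incomplete MLAS; review + complete MLAS) with 'review, no MLAS' as reference. This is preferable because it keeps all patients in the model.
2. State that the MLAS model is fitted in reviewed patients only.

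Either removes the q × R term. In addition:

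- Adjust for age and deprivation, which SAP 10.1 expects to be associated with outcome, and confirm that time since stroke is carried over from the primary model.
- Align the level names: the model uses yes, partial and no, while the definitions use complete, incomplete and no.
- Report the MLAS contrasts as associations, since self-selection into MLAS remains.

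The cost is a wording change and one recoded variable. Review attendance is already an analysis variable, and MLAS attendance is recorded for every participant (protocol 10.3). The reference group shrinks, so intervals widen. For example, with 368 patients followed up in the arm (23 × 16), u = 30%, 15% complete and 10% incomplete (all three assumed), the reference falls from 276 to about 166, against about 55 complete attenders. Ignoring clustering, the standard error grows by √[(1/55 + 1/166) / (1/55 + 1/276)] ≈ 1.05, or about 5%. A larger q would cost more.

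### SAP 10.2.1: the weighted-kappa formula as printed contradicts its own stated scale, and the fidelity bands leave a score of exactly 50% unclassified

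*SAP*

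**What the plan says.** SAP 10.2.1, item 3 (Intervention fidelity), sets out checklists for training and structured reviews. Each item scores 0, 1 or 2 points. For the delivery checklist, for example, "Audio-recorded structured reviews will be scored against a pre-specified checklist (n= 9 items"). The IPCAS training checklist has 16 items and the MLAS training checklist 205.

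Rater reliability of the training and delivery data "will be assessed using percent agreement and Cohen's Kappa (95% CI"). The formula shown is `kappa_w = Σ v_ij·p_oij / Σ v_ij·p_eij`. The definitions beneath it are:

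- v is a "disagreement weight (quadratic weights").
- The observed term "is the proportion of the joint judgements".
- The expected term "is the proportion of judgements expected by chance".
- The value runs from -1 to +1, "where +1 represents perfect agreement between raters".

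The next sentence gives the classification: "Intervention fidelity scores between 80-100% are classed as 'high', 51-79% 'moderate' and <50% as 'low". No rounding rule is given, and no other section restates the formula or assigns a score of 50%.

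**The concern.** A disagreement weight is zero where the raters agree and positive where they differ. A ratio built on such weights measures disagreement relative to chance, so it falls as agreement improves. The scale printed under the formula runs the other way. An analyst who coded the ratio literally would report good scoring as poor and chance-level scoring as perfect.

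The bands raise a smaller question of the same kind. A training session or review that scores the midpoint of its checklist has no class, so someone would have to choose low or moderate after seeing the data.

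Both matter somewhat more than usual here because SAP 8.2.2 declines to define a per-protocol population and points to fidelity assessment instead.

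**Working it through.** **Inputs.** All come from SAP 10.2.1, item 3: the printed ratio, quadratic disagreement weights, three ordered response levels, the stated scale, the checklist lengths (9, 16 and 205 items at 0-2 points, so maxima of 18, 32 and 410) and the three bands. The rating tables below are illustrative, since the documents contain no rating data.

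**Weights.** With k = 3 levels, `v_ij = (i-j)²/(k-1)²`. This gives 0 on the diagonal, 0.25 for ratings one level apart and 1 for ratings two levels apart. Write `R = Σ v·p_o / Σ v·p_e`.

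**Step 1: the SAP's own anchor, +1 at perfect agreement.** Every off-diagonal p_o is 0. With margins 0.2/0.3/0.5, Σ v·p_e = 0.25 × 2(0.2×0.3 + 0.3×0.5) + 2(0.2×0.5) = 0.105 + 0.200 = 0.305. So R = 0/0.305 = 0, and the anchor is not reproduced.

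**Step 2: other cases.**

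- Chance agreement: p_o = p_e in every cell, so R = 1.
- Complete opposite disagreement, with half the ratings in each extreme corner: Σ v·p_o = 1 and Σ v·p_e = 2 × 0.25 = 0.5, so R = 2.
- Good agreement, table rows (18, 2, 0), (3, 25, 4), (0, 3, 45) out of 100, which is 88% raw agreement. Σ v·p_o = 0.25 × 0.12 = 0.030. Row margins are 0.20/0.32/0.48 and column margins 0.21/0.30/0.49. Σ v·p_e = 0.25 × (0.0600 + 0.0672 + 0.1568 + 0.1440) + (0.0980 + 0.1008) = 0.1070 + 0.1988 = 0.3058. R = 0.030/0.3058 = 0.098.

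| Case | Ratio as printed | 1 - ratio |
|---|---|---|
| Perfect agreement | 0 | 1 |
| Good agreement (88% raw) | 0.098 | 0.902 |
| Chance agreement | 1 | 0 |
| Complete opposite | 2 | -1 |

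Every term in R is non-negative, so the printed expression can never reach the negative half of the stated scale. The right-hand column matches that scale at both ends. In the 88% table it also equals the agreement-weight form of weighted kappa, `(Σ w·p_o - Σ w·p_e)/(1 - Σ w·p_e)` with w = 1 - v, which gives 0.902.

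**Step 3: could v have been meant as an agreement weight?** Put w = 1 - v into the printed ratio. Perfect agreement with margins 0.2/0.3/0.5 gives 1/(1 - 0.305) = 1.44, and chance still gives 1. This reading does not recover the stated scale either.

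**Step 4: how far the example generalises.** Raw agreement alone does not fix the value. With uniform margins, Σ v·p_e = 0.25 × 4/9 + 2/9 = 1/3. At 88% agreement, R is 0.03/(1/3) = 0.09 if all disagreements are one level apart and 0.12/(1/3) = 0.36 if all are two levels apart. Weighted kappa is then 0.91 or 0.64. The reversal of direction does not depend on the table chosen.

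**Step 5: the bands.** A score of exactly 50% is 9/18, 16/32 or 205/410, and it falls in none of the three.

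| Checklist | Unclassified totals, unrounded | Unclassified totals, rounded to whole percent |
|---|---|---|
| 9 items (max 18) | 9 | 9 |
| 16 items (max 32) | 16 | 16 |
| 205 items (max 410) | 205-209 (50.0-51.0%), 324-327 (79.0-79.8%) | 203-207 (49.5-50.5%) |

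The entry of 51.0% is 209/410 = 50.98%, which is still below 51. Rounding closes the upper gap. At the lower boundary it moves the gap without removing it: 208 and 209 become 51%, while 203 and 204 become 50%. Mean scores, which the SAP also plans to report, can fall anywhere in the gaps.

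**The case against.** **The equation may have been damaged in extraction.** The text was machine-read from PDF, and mathematics elsewhere in the SAP is imperfect: the worked back-transformation in 9.2.1 stops before its result, and some subscripts in 10.1 do not match. A lost one-minus cannot be excluded. This stands as a caveat, although the rest of the fraction and its definitions are intact. The band gap is in plain text and is not affected.

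**The error would probably not reach the results.** This largely stands. The SAP names the statistic and states its range and direction. It plans percent agreement alongside, cites weighted-kappa sources in section 18 and anticipates R Studio or Stata in section 16. A value of 0.098 beside 88% agreement would look wrong at once.

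**The stakes are limited.** This also stands. A reader might infer from SAP 8.2.2 that the trial's ability to tell an ineffective model from an undelivered one is compromised. The documents do not support that. Kappa covers only the reliability of observed or recorded training and delivery. The outcome models in 10.2.1 use review attendance, action-plan category and MLAS compliance, and neither kappa nor the bands enters them.

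**Whole-number limits suggest whole-percent scores.** That is a fair reading, and it closes the 79-80% gap, but it leaves 50% without a class.

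**The gap does not apply to every instrument.** This is correct. The 15-item needs checklist and the 74-item MLAS receipt questionnaires have no 0/1/2 scoring. The point is confined to the 9-, 16- and 205-item fidelity checklists.

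**Conclusion.** Both parts hold as corrections to the SAP text. The printed ratio gives 0 where the SAP says +1, gives 1 at chance, and cannot be negative. One minus the ratio agrees with everything the SAP says about the statistic. This rests on the equation being printed as it was extracted, which the source PDF will settle. The reversal would occur only if the ratio were coded literally.

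The bands leave 50% unclassified under either rounding convention, and leave more scores unclassified if scores are not rounded.

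The size is small. These are descriptive fidelity summaries, and no co-primary estimate, significance level or sample size depends on them. It would be tempting to conclude that fidelity reliability will be misreported, or that 50% clearly belongs with moderate. The documents support neither. The lower band's limit points 50% one way and the middle band's limit points it the other.

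**What to change.** 1. Check the formula in the source PDF. If the leading term is absent there, print `kappa_w = 1 - Σ v_ij·p_oij / Σ v_ij·p_eij` and keep the quadratic disagreement weights and the stated scale.
2. Before analysis, make the bands contiguous. Assign 50% to one band, which is the sponsor's choice, and state whether the cut-points apply to unrounded or whole-percent scores. If unrounded, the limits must also cover 50% to under 51% and 79% to 80%.

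The cost is about two lines of SAP wording, with no new data and no extra staff.

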# 11 Missing Data

The primary analysis will be the ITT participants who are in the primary analysis population. Linear mixed effects models will be used to analyse the co-primary end-points that are repeated measured. One key benefit of mixed effect models is that this type of model can include data from incomplete cases, so missing data does not necessarily preclude a subject's data from the analysis. In this instance, missing data will be dealt with using a missing at random (MAR) assumption on the analysis population. The outcome variable will include baseline, 6months and 12months outcomes. The mixed effect model will have participant id as a random effect (i.e. random baseline) and the fixed factors will be time, included as a factor variable, and treatment indicator. To help the MAR assumption the residuals of the model will be assumed to have autocorrelation (if the data allow an unstructured correlation structure stratified by treatment indicator). Additional baseline covariates will be included in the model that are potential confounders.

If there is a large amount of missing outcome data from the questionnaires, we will do a sensitivity analysis missing outcome data for the primary analysis as described in White et al. (2011) and Sullivan *et al* (2018). For each questionnaire, where guidelines exist for missing data, they will be followed (see Section 11.1).

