10.2. Analysis of Primary Outcome

We will use intention to treat (ITT) methods for the analysis of the primary end-points. A mixed effects model will be used to model each of the co-primary outcomes with a cluster random effect and fixed effects for the intervention and covariates that might potentially confound the relationship. Distributional assumptions will be assessed graphically by residual q-q plots and residual by fitted value plots. To handle the co-primary outcomes, 97.5% confidence intervals will be reported for the two primary treatment effects which are equivalent to having the Bonferonni correction on the planned 5% significance level for a single endpoint.

The missing data will be analysed under the assumptions of missing completely at random and missing at random. Multiple imputation will be used to impute missing outcome data and the various potential predictors of missingness will be included in the imputation model. Additionally, a sensitivity analysis may be used to investigate non-ignorable missingness mechanisms and their influence on the results.

The full details of the statistical analysis will be specified in the statistical analysis plan (SAP).

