#### 8.5 Multi-centre Studies

IPCAS is a multi-centre trial, comprising multiple GP practices. The trial uses a two-level cluster randomised design, with GP practices representing the clusters, and patients nested within GP practice. GP practice is the unit of randomisation. The data will be analysed to reflect the hierarchical nature of the study design using mixed effect models.

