Each data point will be assumed to have an error term that is identically and independently normally distributed with constant variance. These assumptions will be checked using histograms and box plots to look at the distributional form of the primary outcome SIS scores. All assumptions for the linear mixed effects models will be assessed by viewing plots of the residual values and QQ plots. If any of the assumptions of the linear mixed model are violated then the dependent variable, SIS score, may be transformed to normality or if this fails to correct the distributional assumptions, non-Gaussian or semi/non-parametric methods for analysis will be used.

 $Y_{ijk} = \beta_0 X_{0ij} + \beta_1 X_{1ij6} + \beta_2 X_{1ij12} + u_j + \varepsilon_{ijk}$ 

The analysis population for the primary outcome will be all patients with 12-month outcome measure as the mixed effects model assumes missing at random (MAR).

For missing data analysis the following model will be fitted if there is a cluster effect:

Yijk = continuous outcome SIS score (emotion/ handicap domain)

*i* = individual patient

j = cluster/ practice

*k* = 6 month and 12 follow-up scores

 $X_1$  = dummy variable for the intervention treatment group.

X0 = baseline covariates (baseline score, gender, cluster size, time since last stroke at consent)

 $\beta_0$  = intercept which represents the average baseline SIS score for person *i* 

 $\beta_1$  = difference in score between intervention and control groups at 6 months

 $\beta_2$  = difference in score between intervention and control groups at 12 months (primary)

 $u_i \sim N_1(0, \sigma_b^2)$  is the cluster-level random practice effect

$$\begin{pmatrix} Y_{ij0} \\ Y_{ij6} \\ Y_{ij12} \end{pmatrix} \sim MuN \begin{pmatrix} \beta_0 \\ \beta_0 + \beta_1 + X_{ij6} \\ \beta_0 + \beta_2 + X_{ij12} \end{pmatrix}$$

$$\epsilon_{ijk} \sim MuN \begin{pmatrix} 0 \\ 0, \Sigma_0 \\ 0 \end{pmatrix}$$
 is the residual error, and  $\Sigma_0$  initially has an AR1 structure.

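### The repeated-measures model worded in SAP 11 pools the treatment effect over visits, omits the practice effect and conflicts with the missing-data model in SAP 10.1

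*SAP*

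**What the plan says.** SAP 11 sets out a mixed model for the co-primary endpoints under MAR. Its response vector covers three visits: "The outcome variable will include baseline, 6months and 12months outcomes". The only random effect it names is participant, and for the fixed part "the fixed factors will be time, included as a factor variable, and treatment indicator". It then adds baseline confounders and autocorrelated residuals (unstructured by arm if the data allow). It mentions neither an arm-by-visit term nor a practice effect.

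SAP 10.1 contains two other models:

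- **The 12-month model.** Here "a mixed effect model will be fitted with a random effect for general practice".
- **A longitudinal model**, introduced by "For missing data analysis the following model will be fitted if there is a cluster effect". It has separate treatment effects at 6 and 12 months, flags the 12-month one as primary, and includes a practice effect and initially AR1 residuals. No criterion is given for deciding that a cluster effect exists.

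On clustering, Protocol 10.2 says "A mixed effects model will be used to model each of the co-primary outcomes with a cluster random effect", and SAP 8.5 says "The data will be analysed to reflect the hierarchical nature of the study design using mixed effect models".

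**The concern.** The endpoint is each SIS domain score at 12 months, and practices are the unit of randomisation. A missing-data analysis helps only if it estimates the same quantity as the primary analysis, with a valid standard error. The SAP 11 model, followed as worded, does neither in general. A smaller estimate could reflect averaging over visits rather than missingness, and a smaller p-value could reflect ignored clustering. Agreement or disagreement with the primary result could not be interpreted.

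The two sections also serve the same purpose with different models, so two analysts could each follow the SAP and report different results.

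**Working it through.** **1. The two missing-data models side by side**

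| Element | SAP 10.1 | SAP 11 |
|---|---|---|
| Outcomes | 6 and 12 months by the definition of k; the displayed mean vector also has baseline | Baseline, 6 and 12 months |
| Treatment | Separate 6- and 12-month terms | One indicator |
| Visit effect | None shown in the equation | Time as a factor |
| Random effect | Practice, if there is a cluster effect | Participant |
| Residuals | AR1 initially | Autocorrelated, or unstructured by arm |

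**2. Inputs**

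- From SAP 7: 23 practices per arm, mean 20 patients, 20% loss (so 16 analysed per practice, 23 × 16 = 368 per arm), ICC 0.03, CV of cluster size 0.65, effect 0.33 SD, 2.5% significance.
- Assumed, not in the documents: two-sided test (critical value 2.241), within-patient correlation r of 0.5-0.7 under compound symmetry (CS) or AR1, practice variance constant over visits, complete data, total variance 1.

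**3. The plan's own power figure**

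DE = 1 + ((1 + 0.65²) × 16 − 1) × 0.03 = 1 + 21.76 × 0.03 = 1.653. Effective n per arm = 368 / 1.653 = 222.6. SE = √(2 / 222.6) = 0.0948. Power = Φ(0.33 / 0.0948 − 2.241) = Φ(1.24) = 0.893. The plan states at least 90%, so the inputs are reproduced to within a point.

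As a simple benchmark, a 12-month comparison that ignores practices has SE = √(2 / 368) = 0.0737, a ratio of 0.0737 / 0.0948 = 0.778. Type I error is then 8.1% (4.2% if the ICC is 0.01, 12.1% if it is 0.05, nominal if it is 0).

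**4. Coding (a): indicator on at all three visits**

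GLS with visit as a factor plus one arm term weights the visit-specific differences.

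- Weights at 0/6/12 months: 1/3 each (CS); 0.40/0.20/0.40 at r = 0.5 to 0.435/0.13/0.435 at r = 0.7 (AR1).
- The baseline difference is zero in expectation. With equal 6- and 12-month effects, the coefficient is between 0.13 + 0.435 = 0.565 and 2/3 of the 12-month effect, so 0.33 SD reads as 0.19-0.22 SD. If the 6-month effect is half, the factor is 0.50 (for example 1/6 + 1/3), and 0.33 reads as 0.165 SD.
- Variance of the weighted score: (1 + 2r)/3 under CS, (1 + r)/(3 − r) under AR1. Its ICC is 0.03 divided by that: 0.03 / 0.80 = 0.0375 (CS, r = 0.7) to 0.03 / 0.60 = 0.050 (AR1, r = 0.5).
- DE = 1 + 21.76 × ICC = 1.82 to 2.09. SE ratio = 1/√DE = 0.74 to 0.69.
- Type I error = 2(1 − Φ(2.241/√DE)) = 9.6% to 12.1%.

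**5. Coding (b): indicator zero at baseline**

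- The 6/12-month weights are 0.50/0.50 (CS) and 0.60/0.40 to 0.725/0.275 (AR1), with baseline weight −0.40 to −0.70.
- Equal effects give no dilution. If the 6-month effect is half, the factor is 0.725/2 + 0.275 = 0.64 to 0.50/2 + 0.50 = 0.75.
- Subtracting part of the baseline removes much of the practice variance, so the ICC of the weighted score is 0.0075-0.018. DE = 1.16-1.39, SE ratio 0.93-0.85, type I error 3.8-5.7%.

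**6. Simulation check**

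With 46 practices, gamma-distributed sizes (mean 16, CV 0.65) and 4,000 runs per setting, type I error was 9.2-11.4% under (a) and 3.5-5.4% under (b). A separate simulation of coding (a) (CS, r = 0.6, 8,000 runs) gave type I error 9.9%, mean model SE 0.064 against an empirical SD of 0.087, and mean estimate 0.221 when both true effects were 0.33.

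**7. The condition in SAP 10.1**

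If a cluster effect were judged by a 5% F test (assumed; the SAP gives no rule), simulation of 20,000 trials gives power 0.58 at ICC 0.03 and 0.18 at ICC 0.01. At the plan's own ICC, the practice effect would be dropped in about 42% of trials.

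**The case against.** The best defence is that SAP 11 is a loose summary and that the algebra in SAP 10.1 is the real specification. Section 10.1 supplies the visit-specific effects and the practice term, section 11 supplies the time factor, and SAP 8.5 requires the hierarchy to be respected. That may be the intention. But nothing says that 10.1 governs, and section 11 names its own random effect and fixed factors. Reading section 11 as the no-cluster case would explain the missing practice effect but not the missing 12-month term.

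Several narrower points stand:

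- The mean vector in 10.1 has no treatment term at baseline, which favours coding (b), the milder case.
- The definition of k in 10.1 covers only the two follow-up visits, so baseline's double role as covariate and outcome arises only in the displayed vector. That notation may have suffered in conversion from PDF.
- The added baseline covariates could bring the residual ICC below 0.03.
- The model exists to use incomplete cases, while the figures assume complete data.
- This analysis is supportive, so the error rates measure how far the standard error is understated. They are not the trial's confirmatory error rate.

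These points limit the size. They do not make the SAP 11 wording correct or settle which model applies.

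**Conclusion.** The concern holds. As worded, the SAP 11 model does not in general estimate the 12-month effect. It does so only if the indicator is zero at baseline and the 6- and 12-month effects are equal. Its standard error is too small under either coding whenever the practice ICC is above zero, and the plan assumes 0.03. The understatement is 26-31% under coding (a) and 7-15% under coding (b), given the assumed correlations. The conflict with SAP 10.1 needs none of these assumptions, because it is visible in the text.

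The 12-month model in 10.1 carries a practice effect and is not affected. Nor is the multiple imputation in SAP 12, which is a separate sensitivity analysis. The point should be fixed before analysis, but it does not undermine the primary result.

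**What to change.** Keep the 12-month model with its practice random effect as primary. Replace the longitudinal descriptions in SAP 10.1 and SAP 11 with one model, labelled as the MAR analysis:

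- **Outcomes:** 6- and 12-month domain scores, with baseline score as a covariate only. Keeping baseline in the response with a common mean across arms is also legitimate; the SAP should choose one.
- **Fixed effects:** visit, arm, arm-by-visit and list-size stratum.
- **Random effect:** practice intercept, fitted unconditionally, with the cluster-effect condition deleted.
- **Residuals:** correlated within patient, with the structure named.
- **Estimate:** the arm contrast at 12 months.
- **Population:** patients with a baseline score and at least one follow-up score. State that the 12-month model does not use patients who responded only at 6 months.

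The cost is SAP wording and a little programming. No new data are needed and the primary analysis does not change.
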